## 4. Selection and Enrollment of Study Population

Patients who meet all of the following inclusion criteria and none of the exclusion criteria are considered eligible.

## 4.1 Inclusion criteria

- (1) Provision of written informed consent by patients themselves or their legally acceptable representative.
- (2) Age  $\geq$  20 years at the time of consent.
- (3) New diagnosis of ANCA-associated vasculitis (microscopic polyangiitis, granulomatosis with polyangiitis, or renal-limited vasculitis) according to the definition of the 2012 Chapel Hill Conference [15].
- (4) Positive test for either MPO-ANCA or PR3-ANCA with ELISA, CLEIA, or FEIA method.

## [Rationale]

(1) This criterion was included to conduct the trial in compliance with ethical principles, such as the Declaration of Helsinki. In addition, subjects are required to be 20 years of age or older to ensure a certain level of judgement ability, as disease notification is necessary, considering the poor prognosis of the disease being studied.

(2), (3) Based on previous clinical trials concerning the target disease in this study, the most frequently used inclusion criteria were chosen.

## 4.2 Exclusion criteria

- Previous treatment for ANCA-associated vasculitis prior to providing consent to participate in this study
- (2) Glomerulonephritis with eGFR <15 ml/min or pulmonary alveolar hemorrhage that requires oxygen inhalation of 2L/min or more, as a complication
- (3) Any other systemic autoimmune diseases as a co-morbidity (Note 1)
- (4) HIV infection, HBV/HCV infection, or history thereof (Note 2)
- (5) Females who are pregnant, breast feeding, or at risk of pregnancy and not using a medically acceptable form of contraception
- (6) A history of malignancy within the past 5 years
- (7) A history of tuberculosis within the past 1 year
- (8) A history of severe allergic reactions or anaphylaxis to monoclonal antibodies
- (9) A co-morbidity that may require use of glucocorticoids, immunosuppressive agents, biologic agents, plasma exchange, or high-dose gamma-globulin therapy (Note 3)
- (10) Treatment with a B-cell-targeting biologic agents (e.g., rituximab, belimumab) within the past 6

months

(11) Conditions that, in the investigator's opinion, are unsuited for safe conduct of this trial

## [Rationale]

(1) For the same reason as (1) in the inclusion criteria.

- (2) These are severe conditions requiring plasma exchange in addition to the conventional treatment; therefore, patients with these conditions were excluded, as this study is not planned to perform plasma exchange.
- (3) This criterion was set as it can affect the assessment of the treatment effect.
- (4) (10) These were set to ensure the safety of subjects, in reference to the package insert of rituximab and criteria used in clinical trials using other biologic agents.

(Note 1) This does not apply to those with rheumatoid arthritis, scleroderma, or Sjogren's syndrome, that are with no severe symptom and not requiring glucocorticoid therapy.

(Note 2) In cases that are positive for HBV antibodies but negative for HBV-DNA trial participation is allowed under HBV-DNA monitoring, considering that the Japanese local guideline for HBV allows rituximab to be administered to such patients.

(Note 3) Patients with well-controlled bronchial asthma not requiring oral glucocorticoids can participate in the study (inhaled steroids are allowed to use).

#### 4.3 Informed consent procedure

Prior to initiation of the study, principal investigator or co-investigators provide a clear explanation to potential participants using the informed consent form approved by the IRB, and obtain voluntary written consent to participate in the study. When obtaining the consent, potential participants should be given sufficient time to determine, whether or not to participate in the trial, and opportunities to ask questions, which should be fully, answered.

The principal investigator or co-investigators who provided the explanation and study subjects who received the explanation should put their name and affix a seal, or give their signatures with the date to the consent form. If subjects cannot perform this procedure due to, for example, progression of the primary disease, the written consent may be obtained from their legally acceptable representatives, with informed consent of the subject. When study cooperators provided a supplementary explanation, the cooperators shall also put their name/affix a seal or give their signature with the date to the form. A copy of the consent form and information materials used in the informed consent procedure should be given to the subject, and

the original consent form shall be retained in the trial site.

The principal investigator, co-investigators, or study cooperators ask the subjects who provided the consent whether they are currently visiting any other departments or hospitals. If they are visiting other hospitals or departments, attending physicians at those medical settings must be informed of the subject participation in this trial, after obtaining the consent from the subject.

## 4.4 Provision of updating information to study subjects

Principal investigator or co-investigators shall immediately explain important information that is newly obtained and may affect subject's intention to participate, and confirm the subject's intention to continue the trial participation. The principal investigator or co-investigators shall record the date of explanation, the person who provided the explanation, content of the explanation, the intention of continuation, and the date of confirmation in documents such as subject's medical records.

In addition, the principal investigator revises the informed consent form where appropriate. If there are subjects who have already been receiving the study treatment at the time of the revision, the changed contents shall be explained to those subjects, and a new consent must be obtained for the continuation of the participation.

## 4.5 Registration

A central registration system in a case registration center (Data Management office of clinical research center, Chiba University Hospital) will be used to register study sites and subjects. Procedures for site and case registration are as follows;

## (1) Site registration

1) After obtaining approval from IRB or other relevant committee(s), the principal investigator will fax a copy of the notification letter(s) of approval and a request form of site registration to the case registration center.

2) The case registration center will register the site(s) and forward a notification letter of site registration completion to the principal investigator.

## (2) Case registration

1) The principal investigator or co-investigators obtain written consent from study subjects, and confirm that the subject meets the inclusion criteria and does not correspond to exclusion criteria through screening tests. Subjects determined to be "eligible" will be registered. Case registration is carried out on the website. 2) The principal investigator or co-investigators accesses to a designated URL to confirm eligibility determination that requires entering necessary information, and allocation results. When the subject's eligibility is confirmed, study treatment will be initiated in accordance with the allocation.

The principal investigator or co-investigators should not administer the investigational medicinal product (rituximab) until the subject's registration is completed.

## 4.5.1 Instructions for registration

(1) Registration is not allowed after the initiation of protocol treatment without exception.

- (2) Once the patient was registered, the registration is not cancelled (i.e., not deleted from the database), except when there was a consent withdrawal that include refusal of the research use of data. In case of duplicated registration, information entered at the initial registration (registration number, allocated group) is always used.
- (3) When registration error or duplication is found, contact the case registration center immediately.
- (4) Each study site is responsible for calculation of the body surface area and the drug dose. The information of the body surface area and the drug dose from the case registration center at the time of registration is only for double-checking of the values that attending physicians calculated. Make sure that calculations are also done and verified at the site. If the study site hospital's information system uses a different calculating formula for body surface area from the one used in the case registration center (Dubois formula: body surface area (m2) = body weight (kg) 0.425 x height (cm) 0.725 x 71.84  $\div$  10,000), there will be a difference in the calculated dose between hospital information system and the JCOG-adopted equation. In such a case, the principal investigator of the study site will decide which dose to use.

## 4.6 Allocation

At the time of registration, the case registration center randomly assigns a treatment arm.

## [Rationale]

Allocation adjustment factors chosen for this study are the factors found to have significant effect on the prognosis of ANCA-associated vasculitis by previous studies. Indeed, these factors have been used as allocation factors in many clinical trials on vasculitis [7,8].

In random allocation, the minimization method using (1) age at the time of informed consent (<65 years vs  $\geq$ 65 years), (2) renal function (eGFR < 50 ml/min vs  $\geq$  50 ml/min), (3) ANCA (MPO-ANCA vs PR3-ANCA; cases of double positive will be allocated based on the subtype with a higher measured value)

as allocation adjustment factors is used to avoid significant bias. Researchers at participating sites will not be informed of detailed procedures for random allocation.

## 4.7 Pregnancy

To ensure patients' safety, the principal investigator must report pregnancy of the study subjects (including a case of pregnancy test positive) to the coordinating investigator and the provider of investigational medicinal product. Subjects found to be pregnant are subject to follow-up on pregnancy, and outcomes (e.g., spontaneous or artificial abortion, childbirth details, congenital defects, congenital abnormalities, and maternal or neonatal complication) must be confirmed.

## 5. Study medications

For detailed information and handling of study medications, also see package insert. Study medications to be used in this trial are as follows.

## 5.1 Investigational medicinal product (rituximab)

	Figure 1 Structure of rituximab	
	Variable domains of an anti-CD20 moue monoclonal antibody are fused with	
	constant domains of a human IgG.	
	Mouse-derived variable domains	
	Human-derived constant domains	
Dosage form	Intravenous infusion	
Storage conditions	Store in a cool place (2°C-8°C) while avoiding freezing	
Shelf life	30 months	

## 5.2 Storage of study medications

Investigational medicinal products should be stored in a cool place (2°C-8°C) while avoiding freezing.

## 6. Study Procedures

Patients participating in the study will receive administration of 375 mg/m^2 of rituximab once weekly  $\times$  4 times along with glucocorticoids, as remission induction treatment. Participants are randomly assigned to either the high-dose glucocorticoid group (conventional treatment group) or low-dose glucocorticoid group (novel treatment group) at 1:1 ratio. At the time of randomization, study subjects are stratified according to age, renal function, and ANCA subtype.

Defining the day of glucocorticoid commencement as day 1, the first dose of rituximab will be given between day 1 and day 7. The first dose of glucocorticoids is to be given on the day of patient enrollment or the following day. However, with respect to glucocorticoids, administration of prednisolone 0.5 mg/kg/day is allowed during the period from screening to patient enrollment (up to 7 days) depending on physicians' discretion.

#### 6.1 Dosage, dosage regimen, and administration schedule (rituximab)

Rituximab 375 mg/m2 (cut off after the decimal point; calculated based on the body height and weight at the time of screening) as RITUXAN will be administered via intravenous infusion once weekly  $\times$  4 times.

First administration: Administration rate at the beginning is recommended to be at 50 mg/hour and then can be increased by 50 mg/hour every 30 minutes, up to 400 mg/hour.

Subsequent administration: The rituximab infusion can be started at the rate of 100 mg/hour, and increased by 100 mg/hour every 30 minutes, up to 400 mg/hour. To reduce infusion reactions, premedication with oral administration of acetaminophen and diphenhydramine and intravenous administration of 125 mg of methylprednisolone is mandatory at the time of initial administration of

rituximab. Regarding the premedication for the second and subsequent administration of rituximab, it is not mandatory and left to each study site.

## [Rationale]

This administration regimen is identical to the one used in previous clinical trials, and the efficacy and safety have already been confirmed [8]. The dosing regimen is also identical to the one used in Japan, although the standard indication is for relapsing/refractory cases.

Glucocorticoid is orally administered as Predonine (the same dose of water-soluble Predonine can be given via intravenous infusion only when oral administration is difficult). Administration starts on day 1; however, administration of prednisolone 0.5 mg/kg/day is allowed during the period from screening to patient enrollment (up to 7 days) depending on attending physicians' discretion. Doses and tapering schedules from day 1 for both groups are shown in the table below. The dose for the high-dose group is identical to the conventional standard treatment. Only in cases in which BVAS does not reach 0, or CRP and ANCA values are not normalized, the principal investigator/co-investigator can postpone the initiation of the prednisolone discontinuation step (5mg/body/day to drug off in 14 weeks) in the low-dose glucocorticoid regimen. Once the step has been initiated, prednisolone should be discontinued 14 weeks after the initiation of the step.

weeks	Low-dose group	High-dose group
1-2	0.5 mg/kg/day	1.0 mg/kg/day
3-4	0.25 mg/kg/day	0.8 mg/kg/day
5-6	7.5 mg/body/day	0.7 mg/kg/day
7-8	5 mg/body/day	0.5 mg/kg/day
9-10	4 mg/body/day	0.4 mg/kg/day
11-12	3 mg/body/day	0.35 mg/kg/day
13-16	2 mg/body/day	15 mg/body/day
17-20	1 mg/body/day	12.5 mg/body/day
21-24	0 mg/body/day	10 mg/body/day

Prednisolone doses for the low-dose group in weeks 1-4 and for the high-dose group in weeks 1-12 shall be rounded up in increments of 5 mg.

weeks	BW: 40kg	BW: 60kg	BW: 80kg	BW: 60kg
	(Low dose)	(Low dose)	(Low dose)	(High dose)
1-2	20 mg/day	30 mg/day	40 mg/day	60 mg/day
3-4	10 mg/day	15 mg/day	20 mg/day	50 mg/day
5-6	7.5 mg/day	7.5 mg/day	7.5 mg/day	45 mg/day
7-8	5 mg/day	5 mg/day	5 mg/day	30 mg/day
9-10	4 mg/day	4 mg/day	4 mg/day	25 mg/day
11-12	3 mg/day	3 mg/day	3 mg/day	20 mg/day
13-16	2 mg/day	2 mg/day	2 mg/day	15 mg/day
17-20	1 mg/day	1 mg/day	1 mg/day	12.5 mg/day
21-24	0 mg/day	0 mg/day	0 mg/day	10 mg/day
cumulative	707 mg/24 weeks	987 mg/24 weeks	1197 mg/24 weeks	4200 mg/24 weeks
dose				

Actual example;

## 6.3 Maintenance treatment

For remission maintenance treatment during the post-treatment observation period, 1 g/body of rituximab will be administered every 6 months (6, 12, and 18 months). However, if it is difficult to administer a dose of 1 g/body in a single day, it can be administered as two doses of 0.5 g/body (the second dose is

administered within two weeks after the first infusion). In such a case, the first dose should be given at 6, 12, and 18 months, and the second dose should be given within two weeks after the first dose. The rituximab infusion can be started at a rate of 100 mg/hour, and the rate can be increased by 100 mg/hour every 30 minutes, up to 400 mg/hour. The choice of the premedication method is left to each study site. The glucocorticoid tapering regimen is left to the discretion of the principal investigator or co-investigators with no specific restrictions in the high-dose group.

## [Rationale]

The results of previous clinical trials (RAVE and RITUXVAS trials) have suggested that the relapse rate is higher with only one course of rituximab treatment, resulting in requiring some form of remission maintenance treatment. In the Cambridge University cohort, which is one of the largest cohort of ANCA-associated vasculitis patients treated with rituximab, remission maintenance treatment with administration of 1 g/body rituximab every 6 months has been demonstrated to be effective in those who accomplished remission introduction with rituximab combination therapy, although the results have not validated by.

## 6.4 Criteria for terminating the study – stopping rules

The principal investigator or co-investigators discontinue the study when any of the following criteria are met.

(1) When an adverse event, which falls under the dose reduction criteria, occurred even after reducing the dose of the investigational medicinal product to the minimum level and the principal investigator or co-investigators find discontinuation necessary

(2) When an adverse event occurs and makes continuation of administration of the investigational agent difficult, and the principal investigator or co-investigators find discontinuation necessary

(3) When the patient requested discontinuation

(4) When the principal investigator or co-investigators find the investigational medicinal product inappropriate to administer

(5) When the principal investigator or co-investigators find that discontinuation of the investigational medicinal product is necessary

(6) When the patient was found to be pregnant

(7) When the principal investigator or co-investigators determined that the patient is unable to continue participating in the study

The "date of discontinuation" shall be when the principal investigator or co-investigators decided to discontinue the study, rather than when the event causing the discontinuation occurred, except for (3).

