## **10. Statistical Matters**

## **10.1 Analysis sets**

## 10.1.1 Full Analysis Set (FAS)

The full analysis set (FAS) comprises all subjects enrolled in this study that received at least one dose of a study medication after randomization and visited hospital at least once during the treatment period, from which efficacy data are available. However, subjects are excluded if baseline data cannot be obtained. Subjects are also excluded if there is any serious protocol violation (e.g., consent has not been obtained, patient enrolled outside the contract period).

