#### [Rationale]

To demonstrate the non-inferiority in remission induction rate, the necessary number of cases calculated with the following conditions is 63 in each arm:

 $\alpha = 0.025$  (one-tailed),  $1 - \beta = 0.8$ 

(1)Remission induction rate with rituximab + high-dose glucocorticoids = 0.80

(2)Remission induction rate with rituximab + low-dose glucocorticoids = 0.80

Non-inferiority margin=-0.2

Allocation ratio, 1:1.

With a predicted withdrawal rate of 10%, the target sample size was set as 70 in each arm, a total of 140 cases. The induction rates (1) and (2) are based on RITUXVAS study [8] and the Cambridge University cohort, respectively [14].

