## 10.3 Case handling

As a general rule, the coordinating investigator determines how to handle registered cases. When a new problem has arisen, the statistical analysis supervisor or the Efficacy and Safety Assessment Committee discuss and decide how to handle it as needed.

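### Stopping rituximab counts as leaving the study, and the primary analysis set drops some treated patients, so month-6 remission status can be lost for outcome-related reasons

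*Protocol*

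**What the plan says.** Section 6.4, repeated in the synopsis, opens its list of criteria with "The principal investigator or co-investigators discontinue the study when any of the following criteria are met". Criteria 1, 2, 4 and 5 are about the investigational product; criterion 5 reads "When the principal investigator or co-investigators find that discontinuation of the investigational medicinal product is necessary". Patient request (3), pregnancy (6) and inability to continue (7) are listed separately. Section 5.1 identifies the investigational product as rituximab.

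Section 7.3 and the withdrawal column of the schedule in 23.1 give one set of assessments at discontinuation, including BVAS and remission status. Section 7.4 adds a pregnancy test four weeks later for women of childbearing potential. No later efficacy visit is required.

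Section 10.1.1 limits the FAS to patients who received a dose and "visited hospital at least once during the treatment period, from which efficacy data are available". It removes patients without baseline data, and adds: "Subjects are also excluded if there is any serious protocol violation". The two examples given are missing consent and enrolment outside the contract period. Section 10.5 makes the FAS primary for all efficacy assessments and uses the per-protocol set for reference.

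Section 10.3 states: "As a general rule, the coordinating investigator determines how to handle registered cases". Section 10.2 states: "With a predicted withdrawal rate of 10%, the target sample size was set as 70 in each arm, a total of 140 cases".

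**The concern.** Remission is defined by BVAS and prednisolone dose, and the primary endpoint is that status at 6 months. A patient for whom rituximab is stopped because of an adverse event or the investigator's judgement may well have a worse outlook than one who continues. If that patient leaves the visit schedule, the month-6 status is never collected, and no analysis plan can recover it. Separately, a treated patient who dies before any visit with efficacy data is outside the primary set, although that patient plainly did not reach remission.

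Treatment is open label, the stopping decisions are discretionary, and the protocol does not require exclusions to be decided without knowledge of arm. In a superiority trial, loss of this kind threatens validity in general. In a non-inferiority trial there is a particular hazard: if more failures disappear from the experimental arm than from the control arm, the observed difference shrinks and the margin becomes easier to meet.

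**Working it through.** **The plan's own figure.** Inputs from section 10.2: one-sided alpha 0.025, power 0.80, both remission rates 0.80 ("Remission induction rate with rituximab + high-dose glucocorticoids = 0.80"; "Remission induction rate with rituximab + low-dose glucocorticoids = 0.80"), margin 0.2, allocation 1:1.

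n per arm = (1.960 + 0.842)² × (0.8×0.2 + 0.8×0.2) / 0.2² = 62.8, rounded up to 63. Then 63 / 0.9 = 70 per arm, 140 in total. Both figures reproduce. Exact power of the Wald rule at 63 per arm is 80.0%.

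**Effect of losing failures.** The rule in section 10.5.2.1 declares non-inferiority when the lower limit of the two-sided 95% Wald interval for low minus high exceeds -0.2. Assume 70 randomised per arm and true all-patient rates exactly at the margin: 0.60 low (42 of 70 expected remitters) and 0.80 high (56 of 70). Remove a failures from the low-dose arm and b from the high-dose arm. The analysed rates are then

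p_L = 42 / (70 − a) and p_H = 56 / (70 − b).

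The probability of declaring non-inferiority is the sum, over all pairs of counts that satisfy the rule, of Bin(70 − a, p_L) × Bin(70 − b, p_H).

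| Failures lost, low / high | p_L | p_H | Difference | P(declare non-inferiority) |
|---|---|---|---|---|
| 0 / 0 | 0.600 | 0.800 | -0.200 | 2.5% |
| 3 / 0 | 0.627 | 0.800 | -0.173 | 5.5% |
| 4 / 0 | 0.636 | 0.800 | -0.164 | 7.3% |
| 7 / 0 | 0.667 | 0.800 | -0.133 | 14.2% |
| 2 / 1 | 0.618 | 0.812 | -0.194 | 3.1% |
| 7 / 4 | 0.667 | 0.848 | -0.182 | 4.6% |
| 4 / 4 | 0.636 | 0.848 | -0.212 | 1.8% |
| 7 / 7 | 0.667 | 0.889 | -0.222 | 1.2% |

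Equal loss of failures widens the analysed difference and makes a false claim less likely. Only an excess of lost failures in the low-dose arm inflates the error. The protocol gives no split by arm or by outcome, so every row after the 0 / 0 row is a scenario.

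**Power, if withdrawals are counted as non-remission.** If 0.80 is a completers' rate and all of the planned 10% count as non-remission, each arm has 0.9 × 0.80 = 0.72, and 70 per arm gives about 75%. If 0.80 already counts withdrawals as failures, 70 per arm gives about 84%.

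**The case against.** Several points on the other side stand.

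- The two rules partly offset each other. One visit with efficacy data keeps a patient in the FAS. BVAS is scheduled at months 0, 1, 2 and 4, and the discontinuation assessment also records BVAS and remission status. The FAS wording itself therefore removes few patients. A reader might infer that everyone who stops treatment leaves the primary analysis; the text does not say so.
- Section 9.1 divides by the total number of patients. Read literally, an FAS patient with no month-6 assessment is in the denominator and not in the numerator. The protocol does not state this as a rule, but how to score such patients can properly be left to the statistical analysis plan.
- Criteria 1, 2, 4 and 5 concern rituximab, which both arms receive on the same schedule. Induction is four weekly doses and the next planned dose is at month 6, so these criteria bear mainly on the first weeks. None of them names glucocorticoids, the randomised component.
- The examples of serious protocol violation are enrolment faults, not outcomes. Sections 10.3 and 10.4 provide for the statistical analysis supervisor or the Efficacy and Safety Assessment Committee to be involved, and section 16.1.2 settles eligibility before the primary analysis.

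What these points do not answer is the missing follow-up. A scoring rule in an analysis plan cannot supply assessments that the protocol stops requiring, nor admit patients whom section 10.1.1 excludes. The violation list remains open, since its two entries are only examples.

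**Conclusion.** The point holds as a weakness in wording and design that should be fixed. Section 6.4 does not separate stopping rituximab from leaving the study, no month-6 assessment is required afterwards, and the primary set is narrower than all randomised consenting patients. Outcome-related loss is therefore possible under rules that the protocol itself states.

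The size depends on the split between arms. Against 2.5% with no loss, false non-inferiority reaches 14.2% only if seven low-dose failures and no high-dose failures are lost. At 7 and 4 it is 4.6%, and at 7 and 7 it falls to 1.2%. These figures assume the truth at the margin, 70 per arm and that every lost patient is a failure.

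Two stronger readings are not supported. A reader might infer that the plan is biased toward non-inferiority; the documents establish neither the direction nor the amount of differential loss. A reader might also infer that the stated 80% power is wrong. It is not: 63 and 70 per arm reproduce, and the figure of about 75% rests on an assumption about what the 0.80 counts, which the protocol does not settle.

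**What to change.** 1. In section 6.4 and the synopsis, distinguish discontinuation of study treatment from withdrawal from follow-up. No clinical stopping criterion needs to change.
2. State that patients who stop treatment stay on the existing visit schedule to month 6, and to month 24, unless they refuse.
3. Define the primary set as all randomised consenting patients, analysed by assigned arm, with death before month 6 counted as non-remission.
4. Replace the open-ended violation clause with a closed list of exclusions, decided without knowledge of arm before data fixation.

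Scoring of other unassessed patients and a worst-case analysis belong in the statistical analysis plan.

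The cost is protocol wording, a little more follow-up on visits already scheduled, and possibly slightly lower power, which should be checked under whatever scoring rule is adopted.
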